#### 3) Tertiary endpoints

	Biomarker	Technology	Source	Rationale	Time point	Patient group	Planned timing of analysis
	[REDACTED]	[REDACTED]	[REDACTED]	[REDACTED]	[REDACTED]	[REDACTED]	[REDACTED]
	[REDACTED]	[REDACTED]	[REDACTED]	[REDACTED]	[REDACTED]	[REDACTED]	[REDACTED]

[REDACTED]	[REDACTED]	[REDACTED]	[REDACTED]	[REDACTED]	[REDACTED]	[REDACTED]	[REDACTED]
[REDACTED]	[REDACTED]	[REDACTED]	[REDACTED]	[REDACTED]	[REDACTED]	[REDACTED]	[REDACTED]
[REDACTED]	[REDACTED]	[REDACTED]	[REDACTED]	[REDACTED]	[REDACTED]	[REDACTED]	[REDACTED]
[REDACTED]	[REDACTED]	[REDACTED]	[REDACTED]	[REDACTED]	[REDACTED]	[REDACTED]	[REDACTED]
[REDACTED]	[REDACTED]	[REDACTED]	[REDACTED]	[REDACTED]	[REDACTED]	[REDACTED]	[REDACTED]
[REDACTED]	[REDACTED]	[REDACTED]	[REDACTED]	[REDACTED]	[REDACTED]	[REDACTED]	[REDACTED]
[REDACTED]	[REDACTED]	[REDACTED]	[REDACTED]	[REDACTED]	[REDACTED]	[REDACTED]	[REDACTED]
[REDACTED]	[REDACTED]	[REDACTED]	[REDACTED]	[REDACTED]	[REDACTED]	[REDACTED]	[REDACTED]

**CONFIDENTIAL**

[REDACTED]

[REDACTED]

[REDACTED]

For the above table, blood [REDACTED] samples will be taken at the local participating clinical site for either local storage (until the Sponsor confirms shipping requirements and receiving laboratory) or will be shipped to a central analysing laboratory. The Sponsor will define the local storage requirements prior to shipment or will coordinate the shipment of the sample to the central laboratory. Thereafter, storage of remaining samples will be as per Sponsor agreements with the relevant laboratories.

## 8.2 Primary assessments

There are no primary endpoint pharmacodynamic assays for this trial.

## 8.3 Secondary assessments

### 8.3.1 Pharmacodynamic blood biomarkers (secondary)

Please refer to the AST-VAC2 Laboratory Manual for instructions of collection, handling and storage.

Sample collection schemes may be reconsidered during the trial upon collection of emerging pharmacodynamic data.

- If a patient has received injections on less than three vaccination days, research blood sampling at 3, 6 and 12 months may be omitted based on emerging data. The Sponsor will advise clinical sites so that patient visits can be arranged as required.
- If no immune response is seen at the three month time point, later time points may not be analysed. If the patient consents, any remaining samples not yet analysed will be considered a research 'gift' before future research is performed on the sample.

Blood biomarkers will be measured in whole blood or serum according to agreed standard operating procedures (SOPs) and validated methods.

All patients enrolled will be asked to consent to research bloods and the blood amounts from each patient at the various time points are as follows:

Time point	Total amount, whole blood in mL
Pre-screening (HLA analysis)	3
Baseline*	96
Week 3 vaccination*	69
Week 4 vaccination*	69
Week 6 vaccination*	69
2 weeks post last vaccination*	69
3 months post first vaccination*	75
6 months post first vaccination	66
12 months post first vaccination	66

The approximate total volume of blood withdrawn from each patient for will be 585 mL over a 12 month period.

- 378 mL in first eight weeks
- At 3 months, 75 mL
- At 6 months, 66 mL
- At 12 months, 66 mL.

Sampling time points will be subject to change based on emerging data. The Sponsor will confirm any changes with participating sites and subject to either a substantial/non-substantial protocol amendment, based on the changes made.

#### 8.3.1.1 Identification of peptide specific T cells (Secondary assay 2a)

Whole blood will be collected for the identification of peptide-specific T cells using ELISPOT. A 72 mL sample of whole blood will be collected from all patients at baseline, thereafter, 48 mL will be taken prior to the third, fourth and sixth (or final) vaccinations, 2 weeks after the last vaccination and at 3, 6 and

12 months following the first vaccination. The approximate total volume of blood withdrawn from each patient for this analysis will be 408 mL.

8.4 Tertiary/research assessments

[REDACTED]

[REDACTED]

[REDACTED]

[REDACTED]

[REDACTED]

[REDACTED]

[REDACTED]

[REDACTED]

[REDACTED]

[REDACTED]

[REDACTED]

[REDACTED]

[REDACTED]

[REDACTED]

[REDACTED]

[REDACTED]

[REDACTED]

[REDACTED]

[REDACTED]

[REDACTED]

[REDACTED]

[REDACTED]

[REDACTED]

[REDACTED]

[REDACTED]

[REDACTED]

[REDACTED]

[REDACTED]

[REDACTED]

[REDACTED]

[REDACTED]

[REDACTED]

[REDACTED]

[REDACTED]

[REDACTED]

[REDACTED]

[REDACTED]

## 9 ASSESSMENT OF SAFETY

### 9.1 Investigator Responsibilities

The investigator is responsible for monitoring the safety of patients who have enrolled in the trial and for accurately documenting and reporting information as described in the following sections.

#### 9.1.1 Medical Cover

The chief/principal investigator (CI/PI) is also responsible for ensuring patients have access to 24 hour advice and/or care. Patients will be provided with the necessary contact numbers for both normal working and out of hours care. A copy of the protocol must be made available out of hours to ward staff and clinicians on call so that the appropriate advice may be given to the patient, the patient's relative or other care giver (for example general practitioner (GP)). The CI/PI must ensure that should the on call clinician or ward staff require more advice than is in this protocol, that they have access to the Investigator or delegated members of the investigator's team who can answer any questions.

### 9.2 Adverse event definitions

#### 9.2.1 Adverse event

Adverse events for this trial will be graded according to NCI CTCAE version 4.02. In addition, Injection Site Reactions will be graded according to protocol specific grading system as per [Section 9.8](#).

An adverse event (AE) is any untoward, undesired or unplanned medical occurrence in a patient administered an IMP, a comparator product or an approved drug.

An AE can be a sign, symptom, disease, and/or laboratory or physiological observation that may or may not be related to the IMP or comparator.

An AE includes but is not limited to those in the following list.

- A clinically significant worsening of a pre-existing condition. This includes conditions that may resolve completely and then become abnormal again.
- AEs occurring from an overdose of an IMP, whether accidental or intentional.
- AEs occurring from lack of efficacy of an IMP, for example, if the Investigator suspects that a drug batch is not efficacious or if the Investigator suspects that the IMP has contributed to disease progression.

#### 9.2.2 Serious adverse events

A serious adverse event (SAE) is any AE, regardless of dose, causality or expectedness, that:

- results in death;
- is life-threatening\*;
- requires in-patient hospitalisation or prolongs existing in-patient hospitalisation (some hospitalisations are exempt from SAE reporting – e.g. hospital admissions planned prior to the patient entering the trial; overnight stays for planned procedures such as blood transfusions (Section 9.4.1);
- results in persistent or significant incapacity or disability;
- is a congenital anomaly or birth defect;
- is any other medically important event\*\*

\* A life-threatening event is defined as an event when the patient was at substantial risk of dying at the time of the adverse event, or use or continued use of the device or other medical product might have resulted in the death of the patient.

\*\* A medically important event is defined as any event that may jeopardise the patient or may require intervention to prevent one of the outcomes listed above. Examples include allergic bronchospasm (a serious problem with breathing) requiring treatment in an emergency room, serious blood dyscrasias

## CONFIDENTIAL

(blood disorders) or seizures/convulsions that do not result in hospitalization. The development of drug dependence or drug abuse would also be examples of important medical events.

For fatal SAEs, wherever possible report the cause of death as an SAE with a fatal outcome rather than reporting death as the SAE term. When available, the autopsy report will be provided to the Sponsor.

If during the course of the trial, other medically important events are identified and there is a requirement to report specific events outside of the standard criteria, this will be communicated to sites and the protocol will be updated to reflect this.

Other reportable events that must be treated as SAEs are listed below.

- Any AST-VAC2 related adverse event which meets the stopping rule criteria (as outlined in [Section 3.3.3](#)) are considered a trial specific medically important events and therefore an SAE.
- Pregnancy exposure to the IMP. Any pregnancy occurring in a patient or a patient's partner during treatment with an IMP or occurring within six months of the last IMP administration, must be reported to the Pharmacovigilance Department in the same timelines as an SAE. These should be reported even if the patient is withdrawn from the trial.
- Overdose with or without an AE.
- Inadvertent or accidental exposure to an IMP with or without an AE, including for example, spillage of the IMP that contaminates staff.
- Any AE that could be related to the protocol procedures, and which could modify the conduct of the trial.

### 9.2.3 Suspected, unexpected, serious adverse reactions

A SUSAR is a suspected, unexpected, serious adverse reaction. All AEs and SAEs will be assessed by the Sponsor for seriousness, causality and expectedness. The Pharmacovigilance Department will expedite all suspected unexpected serious adverse reactions (SUSARs) to the relevant Competent Authority/Authorities and the relevant Ethics Committee(s) within the timelines specified in legislation (SI 2004/1031 as amended).

### 9.2.4 Determining adverse event causality

The relationship of an AE to the IMP is determined as follows.

#### Highly probable

- Starts within a time related to the IMP administration and
- No obvious alternative medical explanation.

#### Probable

- Starts within a time related to the IMP administration and
- Cannot be reasonably explained by known characteristics of the patient's clinical state.

#### Possible

- Starts within a time related to the IMP administration and
- A causal relationship between the IMP and the AE is at least a reasonable possibility.

#### Unlikely

- The time association or the patient's clinical state is such that the trial drug is not likely to have had an association with the observed effect.

#### Not related

- The AE is definitely not associated with the IMP administered.

*Note: Drug-related refers to events assessed as possible, probable or highly probable.*

## CONFIDENTIAL

The Investigator must endeavour to obtain sufficient information to determine the causality of the AE (i.e. IMP, other illness, progressive malignancy etc.) and must provide his/her opinion of the causal relationship between each AE and IMP. This may require instituting supplementary investigations of significant AEs based on their clinical judgement of the likely causative factors and/or include seeking a further opinion from a specialist in the field of the AE.

The following guidance should be taken in to account when assessing the causality of an AE:

- Previous experience with the IMP and whether the AE is known to have occurred with the IMP.
- Alternative explanations for the AE such as concomitant medications, concurrent illness, non-medicinal therapies, diagnostic tests, procedures or other confounding effects.
- Timing of the events between administration of the IMP and the AE.
- De-challenge, that is, if the IMP was discontinued or the dosage reduced, what happened to the adverse reaction?
- Re-challenge, that is, what happened if the IMP was restarted after the AE had resolved?

### 9.2.5 Expectedness

Assessment of expectedness for AST-VAC2 will be made by the Pharmacovigilance Department against Reference Safety Information in the current version of the IB, current at the time of the event.

## 9.3 Collection of safety information

### 9.3.1 Screening failures

For patients who fail screening, SAEs must be reported to the Pharmacovigilance Department, CDD from the date of consent until the date the patient is confirmed as ineligible.

### 9.3.2 Patients who consent to HLA screening

AEs and SAEs related to the HLA test procedure should be reported from the time of HLA test consent to the time of consent to the main trial. Thereafter, should the patient consent to the main trial, reporting requirements as per [Section 9.3.4](#).

### 9.3.3 Eligible patients

For eligible patients, SAE and AE collection and monitoring will commence at the time the patient gives their written consent to participate in the trial by signing the main trial consent form and will continue until 30 days after the last vaccination (administration of IMP). From this time point until the patient withdraws, dies or completes the trial, new or ongoing AST-VAC2-related AEs will be collected (regardless of whether the patient goes on to other anti-cancer therapies).

Should an Investigator become aware of any AST-VAC2 -related SAEs after the patient has completed the protocol-mandated follow-up period (as specified above), these must also be reported to the Sponsor within the expedited timelines in Section 9.4.

### 9.3.4 Follow-up of AEs and SAEs

Follow-up of AEs with a causality of possible, probable or highly probable will continue until the events resolve, stabilise or the patient starts another anti-cancer therapy.

The Pharmacovigilance Department will make requests for further information on SAEs to the trial site at regular intervals. Requested follow-up information should be reported to the Pharmacovigilance Department in a timely manner and as soon as possible after receipt of the follow-up request. For fatal or life-threatening cases, follow-up information must be reported to the Pharmacovigilance Department as soon as possible.

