### 5.4 Duration of treatment

Treatment should continue so that the patient receives six vaccinations unless (a) the patient asks to be withdrawn, (b) there is evidence of disease progression (as per Immune-Related Response Criteria (irRC) given in [Appendix 3](#)), (c) the patient is experiencing unacceptable toxicity or (d) the investigator feels the patient should stop the vaccinations for any other reason. Other reasons are listed in [Section 11.0](#).

An End of Vaccination visit will be carried out 30 days post the last vaccination day. This visit will document any emerging AEs since the last vaccination. Adverse events present at this visit, attributed to AST-VAC2 (highly probably, probably or possibly related) will be followed up until resolution or stabilisation of these events (even if the patient starts another anti-tumour treatment).

If a patient terminates treatment prematurely, an End of Vaccination visit should be performed within 30 days of the last vaccination day or when the decision is taken to withdraw the patient from further vaccinations or the trial. These patients should also be asked to continue attending hospital for the 3, 6 and 12 month from first vaccination follow-up visits to provide blood samples for immune analysis (unless the patient withdraws consent from further follow up and participation in the trial or if the Sponsor advises that further sampling is not required).

Patients will be asked to attend follow up as per Section 7.4 until the end of trial (EoT) is declared. The 'End of Trial' will be declared when all patients have either withdrawn (see [Section 11.0](#)) from the trial or died, or the last patient has completed their final follow-up visit (5 years post the first vaccination), whichever is the latter.

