### 7.4 Follow-up

#### 7.4.1 3, 6, 9 and 12 months post first vaccination

##### Patients should undergo the following assessments:

- Research blood samples 3, 6 and 12 months (all +/-1 week) post the first vaccination.
- At the above time points, an evaluation of any AST-VAC2 related AEs will also be performed. Assessments can be performed as clinically indicated.
- A further AE evaluation should be performed at 9 months post the first vaccination also. This can be in the form of a phone call to the patient.
- Any concomitant medications relevant to AST-VAC2-related AEs should be recorded.

All new and ongoing AST-VAC2-related AEs should be followed up until resolution or stabilisation, even if the patient goes onto another anti-cancer treatment. SAEs considered related to AST-VAC2 are always reportable regardless of the time elapsed.

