## CONFIDENTIAL

It is acceptable that the HLA testing is performed outside of the 28 day window: important to note that this test will be performed by a central laboratory therefore sites should plan accordingly to ensure that following consent, the sample is taken and shipped to ensure timely reporting in preparation for the proposed first vaccination.

- b) HLA A\*02:01 positive patients will be asked consider consenting to the main trial for trial treatment and enter the screening period.
- c) Vitals to include temperature, seated BP, pulse rate.
- d) WHO PS to be assessed on day of vaccination as well as during screening.
- e) Haematology, biochemistry, CEA and urinalysis: Week 1 vaccination: laboratory tests must be repeated and reported prior to the first vaccination if the results used for enrolment purposes are >7 days prior to the day of vaccination. Thereafter laboratory parameters are to be measured on Day-1 or Day of vaccination. Haematology and biochemistry results do not need to be reported and checked before each vaccination is given.
- f) Follow up for overall survival to be captured for two years post the first vaccination.  
For extended follow up details, see [Section 12.0](#).
- g) Research blood sampling required, pre, during and post treatment – Please see [Section 8.0](#).  
[REDACTED]
- [REDACTED]
- j) Monthly follow-up required ONLY for those AEs and SAEs considered drug-related (highly probable, probable or possible) that are present at time that patient completes the End of Vaccination visit. Monthly follow-up to continue until resolution, to baseline, stabilisation or patient starts another anti-cancer treatment.  
AE evaluation also to be performed as per [Section 7.4](#).
- k) Radiological disease assessment prior to trial start may have been taken prior to informed consent as part of routine diagnostic procedures. Tumour measurements must be reported according to Immune Response Related Criteria (irRC).
- l) AE evaluation according to CTCAE v4.02 and protocol specific grading system for ISR.
- m) Symptom directed physical examination only.
- n) During extended follow up, new and ongoing AST-VAC2 related AEs should be reported and only concomitant medications relevant to these AST-VAC2 related AEs should be recorded.

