5.10 General data conventions

There is only one dose level for this study, as specified in the study protocol. Patients who deviate from the assigned dose and/or schedule will be clearly described in the CSR with regards to their treatment modification and if applicable in the list of protocol deviations (Section 5.4).

Continuous variables will be summarised and presented with summary statistics.

The median OS will be presented.

Categorical variables will be summarised in frequency tables. Percentages in the summary tables will be rounded and may therefore not always add up to exactly 100%.

The convention in Rave is that an unknown day resolves to 1st of the month and an unknown month resolves to January. Dates may be ordered by this; however, CRUK do not perform calculations on unknown dates except as stated below.

Durations of AEs: the start date of an AE is considered as Day 1 of the event and should be included in all duration calculations (i.e. if an AE starts and stops on same day, the duration should be reported as one day).

- For unrelated AEs, those with missing or partially completed end dates will not be excluded from analysis and the duration of the AE will be calculated from the first day of the month (if unknown) or first day of the year (based on RAVE conventions).
- For related AEs, prior to final data lock, an end date will be either i) confirmed AE end date or ii) stabilisation of AE. Cases where this is not possible are if the patient was lost to follow up. If lost to follow-up then the AE would stay as not recovered/not resolved. In this case duration would not be calculated.

Time to onset of AEs from IMP administration: the time to onset should be calculated from the date of the first AST-VAC2 vaccination and AEs occurring within a specific vaccination window (e.g. start date from date of 2nd vaccination to before date of 3rd vaccination) should also have times to onset calculated from the date of the last vaccination administered in that window (e.g. Vaccination 2). Onset time will be

calculated as 0 if the AE occurs on the same day as the dose; however, if the start time is missing, onset time will not be calculated (only applicable when the drug admin has a start time entered).

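### Protocol Section 9.3.4 ends follow-up of vaccine-related AEs when another anti-cancer therapy starts, contradicting Sections 5.4 and 7.4.1 and the end-date convention in SAP 5.10

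*Protocol*

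**What the plan says.** Protocol Section 9.3.4, the section on follow-up of AEs and SAEs, states that follow-up of AEs with a possible, probable or highly probable causality "will continue until the events resolve, stabilise or the patient starts another anti-cancer therapy".

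Other parts of the protocol treat the same trigger differently:

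- Section 5.4, on AEs attributed to AST-VAC2 and present at the End of Vaccination visit: they "will be followed up until resolution or stabilisation of these events (even if the patient starts another anti-tumour treatment").
- Section 7.4.1: "All new and ongoing AST-VAC2-related AEs should be followed up until resolution or stabilisation, even if the patient goes onto another anti-cancer treatment".
- Section 9.3.3, immediately before 9.3.4, on the period from 30 days after the last vaccination until withdrawal, death or trial completion: "new or ongoing AST-VAC2-related AEs will be collected (regardless of whether the patient goes on to other anti-cancer therapies").
- Section 5.5 keeps collection of related AEs going, under Section 7.4, when other treatment is given during follow-up.
- The AE row of the schedule in Section 7.5 carries ongoing drug-related AEs to the end of extended follow-up.

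Footnote j to that row has a narrower rule: "Monthly follow-up to continue until resolution, to baseline, stabilisation or patient starts another anti-cancer treatment". It then adds "AE evaluation also to be performed as per" Section 7.4.

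The SAP builds on the longer rule. Section 5.10 states: "For related AEs, prior to final data lock, an end date will be either i) confirmed AE end date or ii) stabilisation of AE". It names loss to follow-up as the case where this is not possible. The AE then stays unresolved and no duration is calculated.

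**The concern.** Section 9.3.4 and Sections 5.4 and 7.4.1 concern the same kind of event (a related AE still open) and the same trigger (start of another anti-cancer therapy), and they give opposite instructions. Two sites could handle identical patients differently and each point to current protocol text.

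Section 9.3.4 is a natural place for a site to look. Its heading names the topic, and Section 9.3.2 sends patients who go on to main-trial consent to 9.3.4 for their reporting requirements.

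At stake is the later course of a related AE once the patient has moved to further therapy: whether it worsens, how long it lasts and how it ends. The primary endpoint of this first-in-human trial is the frequency, causality and severity grade of AEs, and the product carries five years of safety follow-up. Any truncation would fall on patients who receive later treatment, so it would not be a random subset.

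**Working it through.** No power, alpha or sample-size figure is involved, and the plan states no figure to reproduce. The check sets side by side every provision on when follow-up or collection of related AEs ends.

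| Provision | Activity covered | Effect of a new anti-cancer therapy |
|---|---|---|
| Protocol 9.3.4 | Follow-up of related AEs | Ends |
| Protocol 7.5, footnote j | Monthly follow-up of related AEs present at the End of Vaccination visit | Monthly follow-up ends; evaluation under 7.4 is additional |
| Protocol 5.4 | Follow-up of related AEs present at the End of Vaccination visit | Continues |
| Protocol 5.5 | Collection of follow-up data, including related AEs | Continues |
| Protocol 7.4.1 | Follow-up of new and ongoing related AEs | Continues |
| Protocol 9.3.3 | Collection of new or ongoing related AEs | Continues |
| Protocol 7.5, AE row | Follow-up of ongoing drug-related AEs | No cut-off given |
| SAP 5.10 | End dates of related AEs | Not listed as an exception |

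**Can 9.3.4 be read consistently with the rest?** One could try to separate collecting an AE (9.3.3) from following it up (9.3.4). That fails against 5.4 and 7.4.1, because both speak of following up. The conflict with those two sections is direct.

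**Does footnote j conflict as well?** Not necessarily. It governs only the monthly contacts and keeps Section 7.4 evaluation in place. It can be read as a drop in frequency rather than a stop, and on that reading it fits the AE row.

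**Which contacts remain under the longer rule?** On the nominal schedule, Section 7.4 evaluates related AEs at:

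- 3, 6, 9 and 12 months: 4 contacts;
- 15, 18 and 21 months: 3 contacts;
- two years: 1 contact;
- every three months from then to five years: 36 / 3 = 12 contacts.

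The total is 4 + 3 + 1 + 12 = 20 scheduled contacts for a patient followed to five years. The longer rule therefore needs no new visits.

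**Which outputs could change?** SAP Table 8 counts episodes and patients. An AE already recorded stays counted whenever its follow-up ends. SAP Tables 10 and 11 report the worst grade within an episode, and Outcome Measure 1 counts AEs of Grade 3 or above. An episode that worsened after follow-up stopped would be under-graded there. Duration and outcome would also be incomplete. Under SAP 5.10, an AE closed only because therapy changed has neither a confirmed end date nor stabilisation, and it is not a loss to follow-up, so no convention applies to it.

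**Scale.** With up to eight patients, one affected patient is 1/8 = 12.5% of a full safety set. That shows how much one patient weighs. It does not estimate how many would be affected.

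**The case against.** The strongest reply is that the conflict comes down to one sentence, and the rest of the protocol would usually catch the data. A site would have to follow 9.3.4 and overlook 9.3.3 directly before it, as well as 5.4, 5.5 and the Section 7.4 contacts. Serious events have further protection. Section 7.4.1 makes related SAEs reportable at any time, and the second paragraph of 9.3.4 has further SAE information requested at regular intervals. Related events that meet the stopping criteria in Section 3.3.3, including clinically significant autoimmunity and Grade 3 or 4 injection site reactions, must be reported as SAEs. The planned tables do not summarise AE duration or resolution. Inclusion criterion 1 requires that no other suitable treatment exists, which may limit how many patients start new therapy.

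Most of this stands. It narrows the exposure to the later grade, duration and outcome of mainly non-serious related AEs. It does not remove the contradiction, and Sections 5.5 and 7.4.3 both anticipate later treatment.

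A reader might infer that footnote j also halts all follow-up on the day new therapy starts. Its closing sentence, keeping Section 7.4 evaluation, does not support that.

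A reader might also blame this conflict for the whole gap in SAP 5.10. That convention is equally silent on a related AE still open at death or withdrawal of consent, so the gap is wider than this point.

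**Conclusion.** The contradiction is real and sits in current text: 9.3.4 against 5.4 and 7.4.1, with 5.5, 9.3.3, the schedule AE row and SAP 5.10 on the side of continuing. The consequence is a risk of unknown frequency. It arises only if a site applies 9.3.4, a patient has an unresolved related AE, and that patient starts further therapy. AE counts would be little affected. What could be missed is a later worst grade, which bears on the severity part of the primary endpoint, together with duration and outcome.

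A reader might infer that outcomes are in fact cut off in some patients, or that years of follow-up are lost for each of them. The documents support neither. They give no rate of affected patients, the Section 7.4 contacts and SAE reporting would catch many events, and follow-up under 5.4 and 7.4.1 also ends at resolution or stabilisation.

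It is still worth correcting, because so few patients are planned and the correction is small.

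**What to change.** Reconcile Section 9.3.4 with Sections 5.4, 7.4.1 and 9.3.3 by removing the start of another anti-cancer therapy from its list of conditions that end follow-up. Resolution and stabilisation would remain.

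In footnote j to the schedule, state that only the monthly frequency ends at new therapy and that related-AE evaluation continues at the Section 7.4 contacts. Simply deleting the new-therapy clause from footnote j is not advised, because it would extend monthly contacts through later treatment, and the reconciliation does not need that.

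SAP 5.10 already matches the longer rule and needs no change for this point. The SAP also lists new anti-cancer therapy (listing 16.2.6.4), so later changes in an AE can be read against it.

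The cost is a protocol wording change and a few more follow-up entries at contacts already scheduled. The change concerns safety data collection only, not treatment.
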